## 2 RISK BENEFIT ASSESSMENT

The company has shown potentially beneficial effects of DS102 in clinical endpoints relevant for the treatment of AH, namely reduction of ALT and fibrosis in a number of preclinical mechanistic studies. To date, toxicological studies demonstrate good tolerability of the drug substance in

doses of up to 2000mg/kg in two species. The phase I study conducted in healthy volunteers demonstrated DS102 to be safe and well-tolerated with no SAEs reported over a 28 day dosing period, as has the ongoing phase II study in which DS102 is administered for a 16 week treatment period (blinded data).

Based on the data summarised above a favourable safety profile may be postulated which, in combination with the potential therapeutic effect of DS102 in a disease that currently lacks effective therapies, gives a positive risk-benefit ratio for the conduct of a Proof of Concept Study with DS102 in patients suffering from severe acute decompensated AH.

The burden for patients in this study is minimised by ensuring standard of care is delivered to all patients and supportive care including nutritional support is available.

The target population of the study are at high risk of mortality and significant morbidity. Without experimental treatments that offer an opportunity to improve outcomes, patients with severe AH have a very poor prognosis.

### **3 RATIONALE FOR THE STUDY**

The postulated mode of action of DS102 covering all relevant pathophysiological features of severe acute decompensated AH together with a preclinically and clinically clean safety profile of the compound makes DS102 an ideal candidate to evaluate clinically the effects of DS102 in this life threatening disease, for which no established treatment is available.

## 4 STUDY OBJECTIVES

### *Efficacy Objective:*

- To compare the efficacy of orally administered DS102 versus placebo, in the treatment of adult patients with severe acute decompensated AH.

### *Safety Objective:*

- To compare the safety of orally administered DS102 in the treatment of adult patients with severe acute decompensated AH.

### *Pharmacokinetic Objective:*

- To evaluate the PK of 15(S)-HEPE following orally administered DS102 capsules, in six adult patients with severe acute decompensated AH in an initial pilot phase of the study, followed by trough level assessment of 15(S)-HEPE in all study participants.

## 5 STUDY ENDPOINTS

### 5.1 Primary Endpoint

- Percentage change in MELD score from baseline to Day 28

### 5.2 Secondary Endpoints

- Change in total bilirubin from baseline to Day 7, 14, 21 and 28
- Proportion of patients showing a 25% reduction of bilirubin at day 7, 14, 21, and 28.
- Change in serum Cytokeratin18-M30/M65 from baseline to Day 7, 14, 21 and 28
- Change in AST levels from Baseline to Day 7, 14, 21 and 28
- Change in AST:ALT ratio from Baseline to Day 7, 14, 21, 28
- Change in MDF score from baseline to Day 7, 14, 21 and 28.
- Proportion of patients showing a 25% reduction in MELD score from baseline to Day 7, 14 and 21
- Change in m-SOFA from baseline to Day 7, 14, 21 and 28
- Proportion of patients with a 2-point worsening of m-SOFA from baseline at Day 7, 14, 21 and 28
- Change in hepatic encephalopathy as assessed by West Haven criteria, from baseline at Day 7, 14, 21 and 28 from baseline to Day 28
- Incidence of acute kidney injury over 28 days (defined by requiring medicinal or mechanical support)
- Incidence of variceal haemorrhage, ascites or hepatic encephalopathy over 28 days

### 5.3 Exploratory Endpoints

- Survival at day 7, 14, 21, 28 and 90 using Kaplan-Meier Plot
- Change in GT from baseline to Day 7, 14, 21 and 28
- Change in ALT from baseline to Day 7, 14, 21 and 28.
- Change in Child Pugh score from baseline to Day 7, 14, 21 and 28
- Change in APACHE-II score from baseline to Day 7, 14 and 28
- Change in Lille score from baseline to Day 7, 14 and 28

### 5.4 Safety Endpoints

- Treatment emergent (S)AEs and SUSARs

## 6 STUDY DESIGN

### 6.1 General

This is a randomised, placebo-controlled, double-blind, parallel group, multicentre, exploratory phase II study preceded by an open label pilot phase to investigate the efficacy and safety of orally administered DS102 capsules in patients with acute decompensated AH aged over 18 years.

After the completion of the open-label phase of the study the DSMB will evaluate the safety and pharmacokinetic data and might recommend a dose adjustment for the double blind randomised phase of the study

After the open-label pilot phase of the study during which six patients will be enrolled, two parallel groups of patients will be enrolled into the randomised double-blind phase of the study to compare one dose of DS102 with placebo over a 28 day treatment period. Patients will receive standard of care therapy in addition to their assigned IMP throughout the treatment period of the study. It is planned that 120 evaluable patients, 60 per treatment group, will be randomised.

Both parts of the study, the open label phase and the double blind phase of the study consist of a screening period of up to five days (at the discretion of the investigator), a 28 day treatment period and a follow up period until day 90 after start of treatment. Screening is to commence upon admission to hospital; at the screening visit, after giving informed consent to participate, patients will be assessed using the screening examinations.

A schematic diagram of the overall timeframe of the study is given in Figure 3.

**Figure 3: Study Outline**

Any medication or therapeutic intervention deemed necessary for the patient, and which, in the opinion of the Investigator, do not interfere with the safety and efficacy evaluations, may be continued.

Before the comparative treatment period can commence, patients will complete a baseline assessment of their disease and eligible patients will be randomly allocated to one of the two parallel group treatment regimens in a 1:1 randomisation ratio:

- Treatment group A: 2 x placebo 500mg capsules orally administered twice a day (BD) (four capsules daily) for 28 days
- Treatment group B: 2 x DS102 500mg capsules orally administered BD (four capsules daily) for 28 days

To maintain the double-blind conditions, the DS102 capsule and placebo capsule will be identical in appearance.

## 6.2 Rationale for Study Design and Dose Selection

The study is randomised, placebo-controlled, and double-blinded to minimise bias during the safety and efficacy assessments, preceded by an open label pilot treatment phase to gather pharmacokinetic information in severely impacted patients.

The study consists of a treatment period of 28 days and was designed in order to assess the safety and efficacy of dosing of DS102 BD (total daily dose of 2000mg) in patients with acute decompensated AH.

Studies in rats and dogs treated for up to 26 weeks and 39 weeks respectively have demonstrated 15-HEPE EE did not indicate any significant toxicity and resulted in a NOAEL of 1000 mg/kg/day in both species (CRL-529123, 529139). This information along with the FDA and EMA guidance on first in man study dose calculation and pre-clinical studies formed the basis for the dose selection in the phase I trial.

Doses of up to 2000mg were administered QD for 28 days in the phase I trial to healthy volunteers. The results from the phase I trial indicate that DS102 was safe and well tolerated. The pharmacokinetic profile of the DS102 seen in the phase I trial indicated that administration with food increased the bioavailability of 15(S)-HEPE. An ongoing phase II study includes dosing of up to 2000mg per day with or after food and so far, has shown DS102 to be safe and well tolerated with no related SAEs. The dose selection in this trial is therefore based on the phase I trial and ongoing phase II trial and the intention to characterise the safety and efficacy of up to 2000mg per day given in divided doses with or after food to patients with acute decompensated AH. A dose adjustment may be decided based on the pharmacokinetic and safety data deriving from the open label phase of the study.

## 7 PATIENTS AND SCREENING

In order to participate in this study the patients must meet all inclusion criteria and must not meet any of the exclusion criteria. Inclusion in the trial starts with the informed consent signature. The inclusion and exclusion criteria are to be verified at the screening visit (Visit 1) and at the start of treatment/baseline visit (Visit 2). Patient history of alcohol abuse for at least six months must be documented at enrolment.

### 7.1 Source of Patients

The study population will consist of male and female patients diagnosed with severe acute decompensated AH aged 18 years and over.

### 7.2 Inclusion Criteria

1. Male or female patients aged 18 years and older
2. Total bilirubin of  $\geq 5$  mg/dl ( $85\mu\text{mol/l}$ )
3. Patients with definite or probable AH
4. MELD  $\geq 18$  at baseline visit
5. MDF  $\geq 32$  at baseline visit
6. AST  $>50$  U/L
7. AST:ALT ratio  $> 1.5$
8. Female patients, or female partners of male patients, of child bearing potential must use highly effective birth control methods or have a sterilised partner for the duration of the study. Highly effective birth control methods are defined as methods that can achieve a failure rate of less than 1% per year when used consistently and correctly. Such methods include intrauterine device or sexual abstinence.

Note: A woman is considered of child bearing potential (WOCBP), i.e. fertile, following menarche and until becoming post-menopausal unless permanently sterile. Permanent sterilisation methods include hysterectomy, bilateral salpingectomy and bilateral oophorectomy

Note: Hormonal contraceptives are contraindicated in patients with severe hepatic diseases and are not acceptable as a birth control method in this study

Note: Sexual abstinence is considered a highly effective method only if defined as refraining from heterosexual intercourse during the entire period of risk associated with the study treatments. The reliability of sexual abstinence needs to be evaluated in relation to the duration of the clinical trial and the preferred and usual lifestyle of the subject

9. Patient and/or legally authorised representative must provide informed consent
10. Able to swallow the provided study medication
11. Not eligible for liver transplant during this hospitalisation

### 7.3 Exclusion Criteria

1. Pregnant or lactating females.
2. Spontaneous liver function improvement defined by decrease of bilirubin level and MDF of >10% within 5 days of hospital admission
3. Grade 4 hepatic encephalopathy (West Haven Criteria)
4. Type 1 hepatorenal syndrome (HRS) or a serum creatinine >2 x ULN or the requirement for haemodialysis
5. History of hypersensitivity to any substance in DS102 capsules or placebo capsules.
6. Alcohol abstinence of >6 weeks prior to screening
7. Duration of clinically apparent jaundice >3 months prior to baseline
8. Other causes of liver disease including:
  - a. Evidence of chronic viral hepatitis (Hepatitis B DNA positive or HCV RNA positive)
  - b. Biliary obstruction
  - c. Hepatocellular carcinoma
  - d. Wilsons disease
  - e. Budd Chiari Syndrome
  - f. Non-alcoholic fatty liver disease
9. History of or active non-liver malignancies other than curatively treated skin cancer (basal cell or squamous cell carcinomas).
10. Previous entry into the study
11. AST >400 U/L or ALT >270 U/L
12. Treatment with any experimental drug within 30 days prior to Day 0 visit (Baseline), or 5 half-lives (whichever is longer).
13. Patients who have used dietary supplements rich in omega-3 oromega-6 fatty acids in the four weeks prior to baseline.
14. Patients dependent on inotropic support (adrenaline or noradrenaline), including Terlipressin
15. Active variceal haemorrhage on this admission requiring more than 2 units of blood to maintain haemoglobin level within 48 hours
16. Presence of refractory ascites
17. Untreated or unresolved sepsis
18. Patients with cerebral haemorrhage, extensive retinal haemorrhage, acute myocardial infarction (within last 6 weeks) or severe cardiac arrhythmias (not including atrial fibrillation)
19. Known infection with HIV at screening.
20. Significant systemic or major illnesses other than liver disease that, in the opinion of the investigator, would preclude or interfere with treatment with DS102 and/or adequate follow up.
21. Previous liver transplantation

## 7.4 Screening and Consent

The Investigator will maintain a Patient Screening Log to collect information on all patients who sign an Informed Consent Form (ICF) regardless of whether or not they meet the study eligibility criteria following completion of the screening evaluations. After completion of screening, all patients deemed eligible to take part in this study will be entered onto an enrolment log.

For information on the consent process, refer to Section 13.2

## 7.5 Withdrawal of Patients

Patients have the right to withdraw from the study at any time for any reason, without repercussion. The Investigator must explain this to the patient and that this will in no way prejudice their future treatment. The investigator also has the right to withdraw patients from the study if she/he feels it is in the best interest of the patient or if the patient is uncooperative or non-compliant. It is understood by all concerned that an excessive rate of withdrawal can render the study un-interpretable, therefore, unnecessary withdrawal of patients should be avoided. Should a patient decide to withdraw, all efforts will be made to complete and report the observations, particularly the follow-up examination, as thoroughly as possible.

In the event of patient withdrawal, the Investigator or one of his or her staff members should talk to the patient or in case of hospital discharge contact the patient either by telephone or through a personal visit to determine as completely as possible the reason for the withdrawal, and record the reason in patient's source document and case report form (CRF). A complete final early termination evaluation at the time of the patient's withdrawal should be made with an explanation of why the patient is withdrawing from the study. If the reason for removal of a patient is an adverse event (AE) or an abnormal laboratory test result, the principal specific event or test will be recorded.

Please note: the patient is allowed not to give a reason for withdrawal. If this is the case this must be recorded as well.

Patients who discontinue the study before Day 28 visit and are discharged from the hospital will be asked to come for an early termination visit as soon as possible and have the assessments listed at Day 28 performed. Mortality will be assessed throughout to Day 90.

There will be two main categories for withdrawals from the study: "complete withdrawal" and "withdrawals from investigational product".

### 7.5.1 Complete Withdrawal

Discontinuation of investigational product and all efficacy and safety evaluations. Standard reasons for withdrawing from further participation in the study and from the follow-up visits may be:

- Patient's decision (withdrawal of consent to participate)
- Patient lost to follow-up

### 7.5.2 Withdrawals from Investigational Product

Discontinuation of investigational product, but continued follow-up visits, including efficacy and safety evaluations. Standard reasons for withdrawing from taking further investigational product, but continuing follow-up visits and safety evaluations may be:

- Unacceptable AEs
- Patient request
- Investigator's discretion
- Intercurrent illness
- Pregnancy

Patients who develop Grade 3 or higher National Cancer Institute Common Terminology Criteria or Adverse Events (NCI-CTCAE), or who experience a 2-point worsening of m-SOFA criteria, that is determined to be possibly or probably attributable to the study drug will be discontinued.

## **7.6 Patient Replacement**

Patients who are withdrawn from the study due to AE or lack of efficacy will not be replaced. Patients who are withdrawn for lost to follow up may be replaced.

## **7.7 Protocol Deviations**

All protocol deviations will be reviewed by the medical monitor as and when each violation is detected. Based on this review, a decision on the patient's continuation in the trial will be reached and this decision will be documented as appropriate. Notification will be made to the relevant authorities as required.

If a patient fails eligibility criteria or meets treatment withdrawal criteria then the treatment must be withdrawn.

## **7.8 Stopping Criteria**

Trial will be stopped if more than one patient has a grade 3 or higher AE on the CTCAE scale in any one category that is determined to be possibly or probably attributable to study drug (exclusion evaluation of liver function).

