## 11 ADVERSE EVENTS AND SERIOUS ADVERSE EVENTS

### 11.1 Definitions of Adverse Events

#### 11.1.1 Seriousness

##### **Adverse Events (AE):**

An AE is defined as any undesirable experience occurring to a patient that has signed the ICF and who has taken their first dose of the study drug, whether or not considered related to the IMP(s). All AEs must be recorded in the eCRF, defining relationship to IMP and severity. AEs should also be recorded by the Investigator in the patient file/notes.

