### 11.1.2 Severity

The intensity of an AE is an estimate of the relative severity of the event made by the Investigator based on his or her clinical experience. The following definitions are to be used to rate the severity of an AE:

- Mild: the AE is transient and easily tolerated.
- Moderate: the AE causes the patient discomfort and interrupts the patient's usual activities.
- Severe: the AE causes considerable interference with the patient's usual activities, and may be incapacitating or life-threatening.

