### 11.1.3 Relationship to IMP

The Investigator will establish causality of the AE to experimental treatment. The Investigator should take into account the patient's history, most recent physical examination findings, and concomitant medications.

The following definitions will be used to determine causality of an AE:

- Not related: temporal relationship of the onset of the AE, relative to the experimental treatment is not reasonable or another cause can explain the occurrence of the AE.
- Related: temporal relationship of the onset of the AE, relative to the experimental treatment is reasonable, follows a known response pattern to the treatment, and an alternative cause is unlikely.

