### 11.1.4 Reporting of AEs and SAEs

All AEs must be recorded in the eCRF, defining relationship to IMP and severity.

**As soon as the Investigator is aware of a potential SAE, he/she should contact the pharmacovigilance (PV) contract research organisation (CRO) monitor by phone, fax or e-mail, and, in any case, no later than 24 hours after the knowledge of such a case. The contact information is provided in the ISF.**

At the time of the call, the Investigator must provide, as a minimum requirement, the patient number, birth date, nature of the SAE and a preliminary assessment of causality. The Investigator should follow-up the initial notification of the potential SAE by faxing a copy of the SAE reporting form to the PV CRO at the number provided in the ISF. The faxed SAE reporting form should be sent to the PV CRO within 24 hours of knowledge of such a case.

Follow-up information on an existing SAE that is fatal or life-threatening should be reported by the Investigator to the PV CRO within five days after the initial report. Where appropriate, hospitalisation or autopsy reports should be made available. All SAEs will be followed up until resolution (i.e., asymptomatic, stabilization or death).

AEs should be reported from the first dose of study drug up to and including the follow up period. Following completion of the study, if the Investigator becomes aware of any AE that is potentially related to the IMP the Sponsor should be notified.

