### **13.10 End of Trial**

The end of trial is defined as 'last patient last visit (LPLV)'. LPLV is defined as the date the Investigator reviews the last subject's safety data and determines that no further evaluation is required for the subject to complete the trial.

The study will be prematurely terminated should more than one patient experience a Grade 3 or higher AE on the CTCAE scale in any one category that is determined to be possibly or probably attributable to study drug (excluding evaluation of liver function), or a 2-point worsening of modified m-SOFA score if possibly or probably attributable to study drug.

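### Protocol 7.8 omits the m-SOFA stopping trigger found in 13.10, and both rules rest on a grade and an attribution that the prescribed adverse-event scales do not contain

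*Protocol*

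**What the plan says.** Trial-level rules:

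- Protocol 7.8, the section named for stopping, states: "Trial will be stopped if more than one patient has a grade 3 or higher AE on the CTCAE scale in any one category". The event must be judged possibly or probably due to study drug, and evaluation of liver function is set aside. The section ends there. It has no m-SOFA clause and no reference to 13.10.
- Protocol 13.10 (End of Trial): "The study will be prematurely terminated should more than one patient experience a Grade 3 or higher AE on the CTCAE scale", with the same category, attribution and liver-function conditions. The sentence then continues: "or a 2-point worsening of modified m-SOFA score if possibly or probably attributable to study drug".

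Patient-level rule:

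- Protocol 7.5.2: a patient with a CTCAE grade 3 or higher event, or a 2-point m-SOFA worsening, "that is determined to be possibly or probably attributable to the study drug will be discontinued".

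What is to be recorded for adverse events:

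- Protocol 11.1.4: "All AEs must be recorded in the eCRF, defining relationship to IMP and severity".
- Protocol 11.1.2: "The following definitions are to be used to rate the severity of an AE". The levels are mild, moderate and severe.
- Protocol 11.1.3 has two levels, related and not related. An event is not related where the timing "is not reasonable or another cause can explain the occurrence of the AE".
- Protocol 11.2.1 defines an adverse reaction by a different test: a causal link is a reasonable possibility and cannot be excluded.
- SAP 6.16.1 tabulates the same three severity levels and two relationship levels as Protocol 11.1.2 and 11.1.3.

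CTCAE appears only in the abbreviation list, 7.5.2, 7.8 and 13.10.

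**The concern.** A trial-level stopping rule should read the same wherever it appears, and it should be possible to apply it from the data that the protocol tells sites to record. Neither holds here. The section whose title sends the reader to it for stopping is the one that lacks a trigger. Both versions also depend on two judgements, CTCAE grade and graded attribution, that the adverse-event section does not prescribe.

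The stake is patient safety during the trial. A team that follows 7.8, or that monitors stopping from the prescribed adverse-event coding, could continue when 13.10 says the study ends. The m-SOFA trigger is not remote from the study's concerns: the introduction describes multi-organ failure as a frequent course of the disease, and 2-point m-SOFA worsening is a secondary endpoint.

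**Working it through.** The plan gives no operating characteristic for the stopping rule, so there is no figure to reproduce. The check is a comparison of wording.

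**Step 1: the rules side by side.**

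| Element | 7.5.2 (one patient's treatment) | 7.8 (trial) | 13.10 (trial) |
|---|---|---|---|
| Force | Mandatory | Mandatory | Mandatory |
| Attributed CTCAE grade 3 or higher | Yes | Yes, more than one patient, same category | As 7.8 |
| Attributed 2-point m-SOFA worsening | Yes | Absent | Yes, patient count not explicit |

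**Step 2: apply both trial-level rules to three situations.**

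| Situation | 7.8 | 13.10 |
|---|---|---|
| Two patients with attributed grade 3 events in the same category | Stop | Stop |
| Two patients with an attributed 2-point m-SOFA worsening, but no shared category of grade 3 events | Continue | Stop, on either reading of the count |
| One patient with an attributed 2-point m-SOFA worsening | Continue | Stop if one patient suffices; continue if the count carries over |

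Every stop under 7.8 is also a stop under 13.10, so the rules are nested: following 13.10 satisfies both, and 7.8 is the incomplete one. The second situation can arise because m-SOFA (Protocol 9.1.8) scores five organ systems, so two patients may each worsen through different organs without sharing an event category. In the third, the natural reading of 13.10 carries the count of more than one patient over to the m-SOFA clause, but the sentence does not say so.

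**Step 3: what the rules need against what is prescribed.**

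| Needed by 7.5.2, 7.8 and 13.10 | Prescribed | Link given |
|---|---|---|
| CTCAE grade 3 or higher | Mild, moderate, severe (11.1.2) | None. Severe is defined by interference with activities, not by grade |
| Possible or probable attribution | Related or not related (11.1.3) | None |
| 2-point m-SOFA worsening | Score at Visits 2 to 9 (9.1.8), so the change can be computed | No separate field for its attribution is described |

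On the last row, "An AE is defined as any undesirable experience occurring to a patient that has signed the ICF and who has taken their first dose" of study drug. An m-SOFA worsening may therefore be recorded as an adverse event, and the same two-level relationship coding then applies to it.

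**Step 4: one event through the three standards.** Take an event with plausible timing that may be due to study drug but that the underlying disease could also explain.

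- 11.1.3: another cause can explain it, so it is coded not related.
- 7.8 and 13.10: if judged possibly attributable, it counts towards stopping.
- 11.2.1: the link cannot be excluded, so it is an adverse reaction.

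The same event can thus count towards stopping and yet be absent from the related events in the prescribed coding.

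**The case against.** Part of the capture does exist. Under 7.5.2, every patient whose event could feed either trial-level trigger must come off study drug, so someone has to make the grade and attribution judgement patient by patient, outside the adverse-event coding. Section 7.5 requires the reason for withdrawal in the source document and CRF and, where that reason is an adverse event or abnormal laboratory result, the specific event or test. SAP 6.6 summarises the reasons for stopping treatment, and SAP 6.16.1 counts adverse events leading to discontinuation. Serious events go to pharmacovigilance within 24 hours with a preliminary causality assessment (11.1.4). The DSMB reviews safety data periodically and can recommend termination (13.3). Section 11.1.4 also does not forbid further eCRF fields.

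This stands, and it limits the second half of the point. It does not close the gap. No section says that the grade or the attribution level is written down, and a reason such as investigator's discretion, which 7.5.2 allows, could hide the trigger. The SAP tables are analysis outputs, not stopping rules. Section 13.3 cites neither 7.8 nor 13.10 and gives the DSMB a power to recommend, whereas both rules are mandatory. None of it touches the difference between 7.8 and 13.10.

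A reader might infer two stronger conclusions. The first is that stops will be missed because the necessary data are never collected. The documents do not support this: the eCRF and DSMB charter were not supplied and may hold the fields or the procedure. The second is that a probability of a missed or extra stop can be stated. The documents give no event rates and no dependence between triggers. Any figure would also turn on whether one or two patients trip the m-SOFA clause, and on whether one counts the 60 + 6 = 66 patients on DS102 or all 60 + 60 + 6 = 126. The latter matters because site and trial-conduct staff are blinded to assignment (12.4), so an event in a placebo patient can also be judged attributable.

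**Conclusion.** The inconsistency is established on the text: 7.8 and 13.10 are both mandatory, only 13.10 contains the m-SOFA trigger, and its patient count is not explicit. A team following 7.8 alone would not stop in every case where 13.10 requires it.

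The mismatch of scales is also established as wording: nothing supplied prescribes a CTCAE grade or a possible/probable category in the adverse-event record, or maps the prescribed scales to them. Its consequence is a risk only, reduced by 7.5.2 and 7.5 and dependent on documents not seen.

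No magnitude is claimed, and no primary analysis or sample size is affected. The point should be fixed because it concerns a safety decision rule and can be corrected cheaply. This review takes no position on which rule or scale is clinically right.

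**What to change.** The passages must be reconciled.

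1. State one identical stopping rule in 7.8 and 13.10, or state it once and cross-refer. Say whether the m-SOFA trigger applies and, if so, for how many patients.
2. Either record the CTCAE grade and the attribution category that 7.5.2, 7.8 and 13.10 use, or map them explicitly to the scales in 11.1.2 and 11.1.3 and to the test in 11.2.1. Include how attribution of an m-SOFA worsening is recorded.
3. Check the eCRF and DSMB charter first. If they already hold these items, a cross-reference in the protocol is enough for step 2.

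The choice of rule and scale belongs to the sponsor and the DSMB. The cost is protocol wording, plus one or two eCRF fields or a short mapping table if they do not already exist. No extra visits or procedures are needed.
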